# 4. What is your plan for primary variable analysis?

Primary outcome variable: SBSES score. A one-way ANOVA will be employed to compare mean scar assessment scores between groups.

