# PROTOCOL

### Background

#### 1. Provide the scientific background, rationale and relevance of this project.

There are many surgical wound closure methods commonly used in orthopaedic surgical practice today. These usually involve a combination of braided and monofilament sutures in the subcutaneous fascia and fat as well as the subcuticular layers of the skin. The methods chosen by surgeons vary widely even amongst partners at the same institution for many reasons, including training background and conflicting reports in the literature about optimal techniques. In some cases, these closure techniques can be time consuming and associated with increased rates of poor cosmetic outcomes or complications. Wound management has also become an increasingly important factor in patient satisfaction. There have been new wound closure products to reach the market (Zipline - Campbell, CA and Clozex - Wellesley, MA), claiming to increase the speed of closure, improve patient satisfaction and decrease the rate of complications. These products are FDA approved and both utilize an adhesive backed film to adhere to the skin along with a proprietary mechanism to promote skin apposition and reduce tension during the healing process. They have been shown to be safe and effective treatment options and have been adopted in many practices.

Our study aims to compare a traditional wound closure using both braided and monofilament sutures to the newer wound closure systems. By determining which method provides superior results, we will improve patient outcomes and satisfaction. The study also aims to assess health care value by exploring the costs associated with each closure technique. In addition to material expenses associated with the traditional sutures, we seek to explore if there is a significant difference in the time required to perform each wound closure method. Every minute of anesthesia and operating room utilization is associated with costs borne by the patient and the health care system. By finding which closure method is the fastest and associated with the best outcome we can improve healthcare value.

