# **Objectives/Hypothesis**

The objective of this study is to compare commonly performed wound closure methods in patients undergoing orthopaedic surgical procedures. The primary outcome measure is SBSES score. Secondary outcome measures include wound adverse events, surgical time, patient satisfaction scores, surgeon satisfaction scores and to determine any difference in the costs associated with each of the wound closure techniques. Our null hypothesis is that there will be no significant difference in terms of wound complication rates, patient satisfaction and surgeon satisfaction scores.

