### Subjects

#### 1. Provide target # of subjects (at all sites) needed to complete protocol.

Surgical subjects: 30 Clinicians: 10

2. Describe expected rate of screen failure/ dropouts/withdrawals from all sites.

Surgical subjects: About 36% Clinicians: 0

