# 2. What are the statistical considerations for the protocol?

Primary outcome variable: SBSES scores will be assessed at scheduled post operative visits. The minimal clinically important difference will be defined as 1 point. The null hypothesis is that

there will be no difference between the SBSES scores between treatment groups (one-way ANOVA).

Secondary outcome variables: patient satisfaction with appearance of scar (on scale of 1-10), physician satisfaction with the technique/device (on a scale of 1-10), and presence or absence of adverse events (including infection and reoperation). For the scaled scores, descriptive statistics will be calculated, and means between groups will be compared (one-way ANOVA). A count of the adverse events per group will be tallied.

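### The plan stops at an overall three-group ANOVA: no pairwise difference, interval or primary SBSES visit is specified, so it cannot say which closure method differs from which

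*Combined protocol and SAP*

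**What the plan says.** All references are to the combined protocol and SAP.

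- **Primary analysis** (Statistical Considerations, item 4): "A one-way ANOVA will be employed to compare mean scar assessment scores between groups". Item 2 states a global null of equal SBSES scores across the treatment groups.
- **Arms** (Study Procedures, item 1): three, namely suture control, Clozex and Zipline.
- **Timing** (Statistical Considerations, item 2): "SBSES scores will be assessed at scheduled post operative visits". Study Procedures, item 1, puts these visits at 14-17 days and 10-14 weeks. Neither is called primary.
- **Relevance threshold** (Statistical Considerations, item 2): "The minimal clinically important difference will be defined as 1 point". The sample size table in item 3 has a 1-point row giving 10 per group, and 10 per group is the number the plan wants for analysis.
- **Secondary analyses** (item 5): one-way ANOVA for the two satisfaction scores, with descriptive statistics; one-way ANOVA for average cost; a tally of adverse events. Closure time is multiplied by the operating-room rate to build the cost figure and is not analysed otherwise.
- **Aims** (Background, item 1): "By determining which method provides superior results, we will improve patient outcomes and satisfaction", and "By finding which closure method is the fastest and associated with the best outcome we can improve healthcare value". Objectives/Hypothesis lists time as an outcome in its own right: "Secondary outcome measures include wound adverse events, surgical time, patient satisfaction scores, surgeon satisfaction scores".

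**The concern.** The aims ask which method is better and which is fastest. With three arms, a significant F says only that the means are not all equal. Someone following the plan to the letter would then have to choose a follow-up procedure and one of two visits after seeing the data. Three contrasts could become six. The trial is also unblinded, and the operating surgeon scores the scar, so fixing these choices in advance matters more than usual.

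A null result has the matching problem. With no interval for any pair, a non-significant F could be reported as no difference even though a 1-point difference has not been excluded.

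The 80% power is stated for the ANOVA. Power to name a pair depends on a procedure that the plan has not chosen.

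**Working it through.** **Inputs.** Three equal groups, SD 0.73, alpha 0.05, 1-point difference, 10 analysed per group (Statistical Considerations, items 2 and 3; Study Procedures, item 1). I assume normal scores with a common SD. I also show 12 per group, the smallest size at which Tukey power for a 1-point pair passes 80% (11 per group gives 77%).

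**The plan's own table.** Noncentral-F power for a three-group ANOVA with means (0, d/2, d) gives 4, 6, 12 and 43 per group for d = 2, 1.5, 1 and 0.5. The plan states 4, 6, 10 and 43. For the 1-point row, a two-sample t test gives 10 and means (0, 0, 1) give 9. At 10 per group, power of the F test is 74% for (0, 0.5, 1) and 86% for (0, 0, 1).

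**Power to name a 1-point pair with Tukey.** The standard error is SE = SD × √(2/n), the noncentrality is 1/SE, the critical t is q/√2, and df = 3(n − 1).

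| n per group | SE | 1/SE | q(0.95; 3, df) | critical t | power | half-width q × SD/√n |
|---|---|---|---|---|---|---|
| 10 (df 27) | 0.326 | 3.06 | 3.506 | 2.479 | 72% | 0.81 |
| 12 (df 33) | 0.298 | 3.36 | 3.470 | 2.454 | 81% | 0.73 |

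**How far the choice of follow-up matters** (1-point pair; simulation, 300,000 trials per scenario, for the gated tests and the error rates):

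| Follow-up | n = 10 | n = 12 | Familywise error, all means equal |
|---|---|---|---|
| Tukey | 72% | 81% | 5% |
| t tests only after a significant F | 73% to 80% | 82% to 88% | 5% |
| Unadjusted t tests | 84% | 90% | about 12% |

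The ranges for the gated tests run from means (0, 0.5, 1) to (0, 0, 1).

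**A significant F does not settle which pair.** With means (0, 0.5, 1) at 10 per group, F is significant in 74% of trials. Tukey flags the extreme pair in 72% and each adjacent pair in about 19%.

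**What a non-significant F leaves open.** Simulate equal means, keep the trials where F is not significant, and count intervals for which |difference| + half-width is at least 1 point.

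| | n = 10 | n = 12 |
|---|---|---|
| A given pair, Tukey interval | 55% | 36% |
| A given pair, ordinary 95% interval | 30% | 17% |
| At least one of three Tukey intervals | 78% | 60% |

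**The case against.** The strongest reply is that ANOVA tests exactly the null that item 2 states, that Objectives/Hypothesis speaks only of comparing methods, and that the wish to find the best and fastest method is Background rationale. Pairwise follow-up would be routine, and with three groups, t tests done only after a significant F hold familywise error at 5% with power close to the planned 80%. This is right as far as error control goes. It does not answer the rest: the plan chooses no follow-up, the gated tests give no simultaneous intervals, and the Background is where the trial says what it will determine.

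Four stronger readings are tempting, and the documents do not support them.

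- **ANOVA is the wrong test.** It is a valid test of the stated null and should stay.
- **The 1-point threshold is unused.** It matches the sizing row that leads to 10 per group. What is missing is its use in reading the results.
- **The plan inflates type I error.** The 12% figure belongs to unadjusted t tests, which the plan does not propose.
- **The trial cannot reach 12 analysed per group.** The enrolment and loss figures do not agree. Item 3 enrols up to 20 per group, while Subjects, item 3, enrols 83 in total. The expected loss reads "Surgical subjects: About 36% Clinicians: 0", yet 30/83 is also 36%, so the figure could be the completing share. Depending on the reading, between 20 × 0.36 = 7.2 and 83 × 0.64/3 = 17.7 per group would be analysed. No retention claim can rest on that.

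Group means would also not be wholly hidden: descriptive statistics are planned for the satisfaction scores, and average costs are compared.

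**Conclusion.** The point holds as an omission that should be repaired. No section supplies a pairwise contrast, an interval or a multiplicity rule for any outcome, names a primary SBSES visit, or analyses closure time except through cost. A positive result would not identify a method, and a null result could not be judged against the plan's own threshold.

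The size is moderate. Tukey power at the planned 10 per group is about 8 percentage points below the stated 80% (80 − 72) and is about 81% at 12. A half-width of 0.81 means that an observed difference of only 0.2 points already leaves 1 point inside the interval (0.2 + 0.81 = 1.01).

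The missing specification can be read directly from the text. The figures rest on normal scores, a common SD of 0.73 and equal groups. They are approximate for a 0-5 score whose planning mean is 4.4, close to the upper limit.

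**What to change.** - **Statistical Considerations, items 2 and 4.** Name one primary SBSES visit and make the other secondary. Keep the ANOVA. At the primary visit, add the three mean differences (Clozex minus suture, Zipline minus suture, Clozex minus Zipline) with simultaneous 95% Tukey intervals, and interpret them against 1 point. Tukey is preferred because it supplies intervals, not because the gated tests fail to control error.
- **Item 5.** Report the same three contrasts for the satisfaction scores, cost and closure time, labelled as secondary and without adjustment across outcomes. Report patient satisfaction at the same named visit.
- **Item 3.** State the pairwise power: about 72% for 1 point at 10 analysed per group and 81% at 12 (Tukey, SD 0.73, normal model), with a note that this is approximate on a 0-5 scale with planning mean 4.4.

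**Cost.** A few sentences and no new data, since closure time is already recorded. One analysis is added (closure time), and the stated power becomes less favourable. When a true 1-point difference exists, about 2% of significant F results at 10 per group would name no Tukey pair (1.9% under both mean patterns), and the plan should say how that outcome will be reported.

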# 5. What is your plan for secondary variable analysis?

Secondary outcome variables: patient satisfaction with appearance of scar (on scale of 1-10), physician satisfaction with the technique/device (on a scale of 1-10), and presence or absence of adverse events (including infection and reoperation). For the scaled scores, descriptive statistics will be calculated, and means between groups will be compared (one-way ANOVA). A count of the adverse events per group will be tallied.

Cost analysis between approaches will be assessed using the following metrics: the cost of operating room time per minute will be multiplied by the time for closure and added to the cost of materials to determine a total cost for each approach. The average costs for each approach will be compared using a one-way ANOVA to determine if there are significant differences in costs.

# 6. Have you been working with a statistician in designing this protocol?

Version Date: 07-29-22 Page Number: 4 of 8

YES

IF YES, what is their name? [name]

# 7. Will data from multiple sites be combined during analysis? NO

# **Study Procedures-Biomedical Research**

### 1. What will be done in this protocol?

Patients who meet above inclusion criteria and provide informed consent will be enrolled in the study. All members of the research team that will be assisting with the surgical closure (including attending surgeons, fellows, residents and/or physician assistants) will receive full training in the application of both the Clozex and Zipline devices to insure uniform experience among participants. The clinicians performing the closure are also investigators in this research and may opt out of participating in this study. There are no pre-operative study procedures for the patients, aside from a review of inclusion and exclusion criteria and enrollment.

On the day of surgery, the enrolled subject will be randomized into one of three study groups. The randomization will occur during surgery, prior to wound closure. The circulating nurse will open an envelope, which will determine the randomization group for the subject. This will allow operating room staff the time to assemble the appropriate materials for closure depending on participant's group assignment without any delay to standard of care. The subjects' randomization into a treatment group is not expected to significantly increase the time of the operation or duration of anesthesia. The wound closure will proceed as follows:

- 1. Any deep fascial layers will be closed with braided Vicryl suture as indicated and according to standard of care.
- 2. The subcutaneous fat will be closed using 3-0 Monocryl in inverted, interrupted fashion according to standard of care.
- 3. The circulator will then start a timer that will run until the wound is completely closed.
  - A. If randomized to the **Control group**: Closure will proceed with a running 3-0 Prolene subcuticular suture with escape stitches.
  - B. If randomized to the **Clozex treatment group**: Closure will proceed with application of the adhesive device according to manufacturer's recommendations
  - C. If randomized to the **Zipline treatment group**: Closure will proceed with application of the adhesive device according to manufacturer's recommendations
- 4. If at any time, the surgical provider (attending surgeon, fellow, resident, PA) determines that the device in the test group has failed (i.e. adhesive failure, device breakage), s/he may elect to proceed with suture closure and study cross over shall be recorded.
- 5. At the conclusion of the wound closure, the timer will be stopped and the operative time will be recorded.

Version Date: 07-29-22 Page Number: 5 of 8

Dressings will then be applied in standard fashion including 4 x 4 gauze, webril wrap and ACE bandage and splinting as indicated. The team member who performed the wound closure (attending surgeon, fellow, resident or PA) will fill out the survey on satisfaction with the closure (scale 1 - 10) and note any complications or confounding factors (challenging incision pattern or application problems). The subject will be discharged with standard wound care instructions to keep the surgical dressing in place for 3 days and then to replace it with clean sterile dressings. The subjects will be cautioned not to submerge their wound underwater for at least 2 weeks following surgery, as per standard protocol.

Initial follow up will occur at a standard time interval within 14 - 17 days after surgery, at which point Prolene sutures will be cut and removed and Clozex/Zipline devices will be removed. An assessment of the wound will take place by the same attending surgeon who performed the procedure using the Stony Brook Scar Evaluation Scale (SBSES) using the below rubric (scale 0 - 5).

| Category                 |   | Points |
|--------------------------|---|--------|
| Width                    | > 2 mm  | 0      |
|                          | ≤ 2 mm  | 1      |
| Height                   | Elevated/ depressed in relation to surrounding skin | 0      |
|                          | Flat  | 1      |
| Color                    | Darker than surrounding skin                        | 0      |
|                          | Same color or lighter than surrounding skin         | 1      |
| Hatch marks/Suture marks | Present   | 0      |
|                          | Absent  | 1      |
| Overall appearance       | Poor  | 0      |
|                          | Good  | 1      |
|                          |   |        |

A brief survey will then be completed by the study participant to rate their satisfaction with their surgical scar on a 1 - 10 scale. The physician or physician assistant seeing the subject in follow up will document the presence or absence of adverse events (including infection and reoperation).

The SBSES assessment, adverse event monitoring and patient satisfaction will be recorded at a second standard of care follow up visit between 10 - 14 weeks after surgery. The subject will be released from the study after the final standard of care follow up visit occurs, and will no longer need surveillance or monitoring.

Cost analysis between the groups will be assessed using the above statistical approach. To carry out this analysis, we will obtain: 1. Cost for all materials needed for wound closure, 2. Amount of time (in minutes and seconds) needed to close the wound (start time = all supplies are gathered to close the wound, and stop time = wound is declared fully closed), and 3. Operating room costs (including overhead) per minute.

Version Date: 07-29-22 Page Number: 6 of 8

2. If this protocol involves study treatment, explain how a subject will be transitioned from study treatment when they have completed their participation in the study.

The patients that are involved in the study treatment groups will have the same post operative management as the control group. At the 2 week visit, the devices (Clozex or Zipline) will be removed and all groups will have the same wound care instructions.

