### **Inclusion/Exclusion Criteria**

### 1. List the criteria for inclusion

Surgical Subjects:

- Age 18+
- Patient scheduled to undergo elective orthopaedic surgical procedure with a minimum anticipated incision length of 3 cm.
- Willingness and ability to comply with scheduled visits and study procedures.

Clinicians:

Version Date: 07-29-22 Page Number: 2 of 8

- Attending surgeons, physician assistants and trainees (fellows and residents) in the orthopaedic surgery department
- Willingness to comply with randomization and study protocols

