# 2. List the criteria for exclusion

Surgical subjects:

- Revision Surgery
- Compromised wound healing (autoimmune disorder, chronic steroids )
- Pregnant women, fetuses, neonates, children, prisoners, cognitively impaired, educational or economically disadvantage, non-English speaking subjects.
- Currently taking Immune modulating (DMARD) medications will exclude patient from participation in study
- Currently taking Chronic Steroids

Clinicians:

- None
- 3. List any restrictions on use of other drugs or treatments.

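### Nothing confirms, before the allocation envelope is opened, that the wound suits all three closures, while failure and crossover are defined only for the device arms

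*Combined protocol and SAP*

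**What the plan says.** - **Inclusion criteria.** The one criterion that describes the incision is a "minimum anticipated incision length of 3 cm". It is a forecast made before surgery.
- **Exclusion criteria.** Those that bear on the wound are "Revision Surgery", "Compromised wound healing (autoimmune disorder, chronic steroids"), current chronic steroid use, and DMARD use ("Currently taking Immune modulating (DMARD) medications will exclude patient from participation in study"). None mentions the shape or site of the incision, or whether the skin can take an adhesive.
- **Background, item 1.** Of the two devices, the plan says that they "both utilize an adhesive backed film to adhere to the skin".
- **Study Procedures, item 1.** Before surgery, the only study steps for patients are the review of criteria and enrolment. In theatre, "The randomization will occur during surgery, prior to wound closure". The nurse opens the envelope, and no check of actual length or suitability comes first.
- **Study Procedures, step 4.** If the provider judges that a test-group device has failed, the wound may be sutured and a crossover is recorded. Control has no corresponding rule.
- **After closure.** Whoever closed the wound completes a survey and is to "note any complications or confounding factors (challenging incision pattern or application problems"). This applies in every arm.
- **Statistical Considerations, items 2, 4 and 5.** Groups are compared by one-way ANOVA. No analysis set and no rule for crossovers are given.

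**The concern.** The envelope is opened when the actual incision is in view, which is the best moment to ask whether any of the three closures could be used. The plan does not ask. It expects that some incisions will be awkward for a device, because the survey has a place to say so, but that information arrives after allocation.

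A wound that an adhesive film cannot properly close has a two in three chance of allocation to a film. There, its unsuitability can show up as a device failure and a change of treatment. In the control arm the same wound is sutured as assigned and no departure arises. The asymmetry follows from the rules, whatever its frequency.

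The primary comparison is at stake. With crossovers kept in their assigned arm, a device arm mixes device and suture closures and its SBSES contrast with control is diluted. With crossovers dropped or moved to the arm of the treatment received, difficult wounds would leave the device arms only, and the groups would no longer be comparable. The plan does not say which would be done.

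**Working it through.** **1. Order of events.** Eligibility review (before surgery), then envelope (in theatre), then closure, then failure and crossover (device arms only), then survey note on difficult incisions (all arms). The actual incision can be judged from the second step on, but the plan first records anything about it at the fourth and fifth.

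**2. The plan's own figure.** Inputs from Statistical Considerations, items 2 and 3: SD 0.73, smallest important difference 1 point, alpha 0.05, power 0.80, 10 per group. The standardised difference is 1/0.73 = 1.37. A two-sided two-sample t test needs 10 per group, which matches the plan. A three-group ANOVA needs 9 if one group differs from the other two, and 12 if the third mean lies midway. The stated 10 is therefore reproduced closely enough to serve as the base.

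**3. Dilution of SBSES.** Let u be the share of device-arm subjects who cross to suture. The documents give no value, so the values below are assumed. If those subjects score like controls and are analysed as randomised:

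observed contrast = (1 − u) × 1 point.

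For the t test with 10 per arm (18 degrees of freedom), the noncentrality is (1 − u)/0.73 × √(10/2), which is 3.06 at u = 0 and 2.45 at u = 20%. Results:

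| u (assumed) | Contrast | Power, t test | Power, ANOVA, both devices differ equally from control |
|---|---|---|---|
| 0 | 1.00 | 82.5% | 85.8% |
| 5% | 0.95 | 78.6% | 81.9% |
| 10% | 0.90 | 74.1% | 77.3% |
| 20% | 0.80 | 64.0% | 66.6% |

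In an arm of 10, one crossover is u = 10% and two are u = 20%.

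**4. Chance of meeting the problem at all.** With 2 × 10 = 20 analysed device subjects, P(at least one crossover) = 1 − (1 − u)^20, which is 64%, 88% and 99% at u = 5%, 10% and 20%.

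**5. Time and cost are different.** One timer runs from the end of the subcutaneous layer until the wound is closed (steps 3 to 5). A crossover therefore carries the failed attempt plus the suturing, and the materials of both. The time contrast is (1 − u)Δ − u × (time of the failed attempt), where Δ is control time minus device time. An illustration with assumed values: control 1.0, device 0.5, failed attempt 0.5, u = 20%. The device-arm mean is 0.8 × 0.5 + 0.2 × (0.5 + 1.0) = 0.70. The contrast is 1.0 − 0.70 = 0.30 instead of 0.50, a loss of 40% where simple dilution would give 20%. An individual crossover (1.5) takes longer than a control closure (1.0).

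**The case against.** **The trial may be meant to be broad.** The objective is to compare closures in orthopaedic patients generally, and device failure in ordinary elective incisions can be a legitimate part of that comparison. This stands for failures that nobody could foresee. Step 4's examples, loss of adhesion and breakage, are of device performance, and the proposed check would not remove them. It is weaker for wounds that the surgeon can already see are unsuitable.

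**A check adds discretion.** The clinicians who close the wounds are investigators, and the attending surgeon later scores the scar unblinded. But a judgement made while the envelope is sealed cannot depend on the assignment, so it falls on all arms alike. One caution stands: the list is forced to equal numbers and allocation is open once revealed, so the last assignments could be partly guessed. Reasons for screen failure should be logged.

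**Envelopes are tied to study numbers.** A sealed envelope would waste a slot and disturb the equal groups unless it is reused. This stands, and the fix deals with it.

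**Stronger readings to resist.** A reader might infer the following:
- *Eligibility rests on anticipated length alone.* It does not. The exclusions for revision surgery, impaired healing, steroids and DMARDs also bear on the wound. Length is only the sole criterion about the incision itself.
- *Difficult control wounds go unnoticed.* The survey is completed by whoever closed the wound, in any arm. Only failure and crossover are one-sided.
- *Subjects known to react to adhesive are being exposed.* The documents report no such reactions, and device application follows manufacturers' recommendations that are not reproduced and may cover this. What can be said is that the listed criteria are silent on it.

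**Conclusion.** The gap is real and can be read directly from the text: no recorded confirmation before the envelope that the wound suits all three closures, and failure and crossover defined in two arms of three. Opening the envelope late is a strength of the design. The fault is that the opportunity it gives is not used.

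The size is conditional. That unsuitable wounds will be randomised is a reasonable inference from the survey wording, but no frequency is documented. The fall in power from 82.5% to 78.6%, 74.1% and 64.0% holds for SBSES only, and only if the crossovers score like controls and are analysed as randomised. It is tempting to say that time, cost and satisfaction shrink toward control by the same share. The single running timer contradicts this for time and cost, and nothing in the plan supports it for the closer's satisfaction after a failed device.

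This is a cheap improvement worth making before enrolment. It does not by itself invalidate the trial or change the stated sample size.

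**What to change.** - **Before the envelope.** Immediately before it is opened, the surgeon records that the actual incision meets the length criterion and that the subject and incision are suitable for any of the three closures. What counts as suitable, including skin tolerance of adhesive, is for the investigators to define.
- **If not confirmed.** The envelope stays sealed, a screen failure is logged with its reason, and that envelope is used for the next eligible subject. One sentence under Statistical Considerations, item 1, should say so, because envelopes are currently prepared by study number.
- **After allocation.** State that all subjects are analysed in the group to which they were randomised, and report crossovers by arm with the reason.

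The cost is one eligibility line, one intraoperative tick-box and two sentences of analysis text. The downside is a slightly narrower population and a few more screen failures. The plan's allowance of about 36% covers screen failures, dropouts and withdrawals together, so it should not be assumed to have room to spare.

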# **Statistical Considerations**

# **1.** Is stratification/randomization involved? YES

# ► IF YES, describe the stratification/ randomization scheme.

Simple randomization will be used. A random number generator will be used to devise a list to assign study numbers to treatment groups, ensuring that there will be equal numbers assigned to each group. No other variables will be used for stratification. For each study number, the treatment assignment will be placed into an envelope by the clinical trials coordinator and sealed.

There will be no blinding of subjects or personnel involved in the study once the envelope with group assignment has been opened.

The statistician doing the randomization and the clinical trial coordinator will be the only ones with access to the master treatment assignment list.

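### The envelope is opened before the layers common to all arms are closed, so the closing clinician can know the arm during those steps: a performance-bias risk of unknown size that is cheap to reduce

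*Combined protocol and SAP*

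**What the plan says.** All references are to the combined protocol and SAP.

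- **When the arm is revealed.** Study Procedures, item 1: "The randomization will occur during surgery, prior to wound closure". Also: "The circulating nurse will open an envelope, which will determine the randomization group for the subject". The reason given is practical: "This will allow operating room staff the time to assemble the appropriate materials for closure depending on participant's group assignment".
- **What closure consists of.** The same item lists the steps. Step 1: "Any deep fascial layers will be closed with braided Vicryl suture as indicated and according to standard of care". Step 2: "The subcutaneous fat will be closed using 3-0 Monocryl in inverted, interrupted fashion according to standard of care". Only step 3 (Prolene, Clozex or Zipline) differs by arm.
- **Blinding.** Statistical Considerations, item 1: "There will be no blinding of subjects or personnel involved in the study once the envelope with group assignment has been opened".
- **Timing.** After step 2, "The circulator will then start a timer that will run until the wound is completely closed". Later in the same item, the cost paragraph defines the interval differently: "start time = all supplies are gathered to close the wound, and stop time = wound is declared fully closed".
- **Use of the time.** Statistical Considerations, item 5 multiplies closure time by the operating room cost per minute and adds the cost of materials. Study Procedures, item 1 counts all closure materials.

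**The concern.** Steps 1 and 2 are meant to be a common base on which three skin closures are compared. They come after the envelope is opened, and nothing in the plan keeps the arm from the person suturing until step 3. Step 1 is discretionary. Step 2 fixes the material and the stitch type, but not how many stitches are placed, how far apart or how tight. A clinician who knows that an adhesive device will follow could, without intending it, support the deeper layers differently from one who is about to run a subcuticular suture.

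Three results are exposed. SBSES is exposed because support of the deeper layers could plausibly affect the width and height items. Material cost is exposed because the deep and subcutaneous sutures count as closure materials. Closure time, and the cost derived from it, is exposed in a way that depends on which timer definition is used. The plan neither records stitch counts or duration for steps 1 and 2 nor compares them by arm, so a difference could be neither seen nor allowed for.

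**Working it through.** **Sequence.** The order in the text is: envelope opened by the nurse; materials assembled by arm; step 1; step 2; timer; step 3. Personnel are unblinded from the first event on. So the clinician can know the arm in steps 1 and 2. No sentence says that the clinician is told at that moment. This is inferred from the opening in the operating room, the arm-specific assembly of materials and the no-blinding statement.

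**Timer.** The two start points lead to different consequences:

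| Start point | Are steps 1–2 timed? | Effect of extra work in steps 1–2 on recorded time |
|---|---|---|
| Step 3: after step 2 | No | Indirect only, for example if closer subcutaneous apposition makes the skin step quicker or slower |
| Cost paragraph: when supplies are gathered | Possibly, since gathering may finish before step 1 | Direct: extra stitches lengthen the recorded time |

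**SBSES illustration.** Inputs: SD 0.73, mean 4.4, alpha 0.05, power 0.80, one-way ANOVA and 10 analysed per group out of up to 20 enrolled (Statistical Considerations, item 3); three arms (Study Procedures, item 1); scale 0–5 (the rubric there).

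*The plan's own figure first.* For a 1-point difference the plan states 10 per group. With the third mean midway, the three-group ANOVA needs 12 (power at 10 is 0.739). With one arm differing from the other two, it needs 9 (power at 10 is 0.858). A two-sided t test gives 10. The stated figure is within 2 patients of each, and nothing below depends on it.

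*Rejection rate when skin closure has no effect.* Suppose technique in steps 1–2 shifts mean SBSES by s in both device arms, or in one arm only. The sum of squared deviations of the three means is the same in either case, (2/3)s². The noncentrality is

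λ = n × (2/3)s² / SD², with SD² = 0.73² = 0.5329.

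The rejection rate is the probability that a noncentral F with 2 and 3n − 3 degrees of freedom exceeds its 5% critical value (3.354 for 2 and 27 df; 3.159 for 2 and 57 df).

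| Assumed s | n per group | λ | Rejection rate |
|---|---|---|---|
| 0.1 | 10 | 0.125 | 5.9% |
| 0.25 | 10 | 0.782 | 10.7% |
| 0.1 | 20 | 0.250 | 6.8% |
| 0.25 | 20 | 1.564 | 17.7% |

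More patients do not dilute the bias. They make it more likely to be declared significant.

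*How large can an upward shift be?* From a mean of 4.4 the average patient has 5 − 4.4 = 0.6 points to gain over all five items. A shift of 0.1 recovers 0.1/0.6 = 17% of that, and 0.25 recovers 42%. A rise of 0.5 would put the mean at 4.9. On a 0–5 scale the SD at that mean cannot exceed √(4.9 × 0.1) = 0.70, which is below the 0.73 assumed. For that reason I do not carry the illustration to 0.5.

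**The case against.** **The comparison may be of whole methods.** The objective is to compare commonly performed wound closure methods, and the control is described as a full layered closure. In practice a surgeon knows the planned skin closure while closing the deeper layers, so adaptation could be seen as part of the method. This has some force, but the plan points the other way: steps 1 and 2 are written identically for every arm, only step 3 is arm-specific, and the step 3 timer starts when the shared layers are finished.

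**Room to differ is limited.** Material is fixed in both steps, stitch type is fixed in step 2, and both follow standard of care. This stands and narrows the risk. It does not remove it, because count, spacing, tension and the decision to close fascia remain open.

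**A larger bias is untouched.** The operating attending surgeon scores the SBSES unblinded. True; that is a separate matter, and this change does not address it.

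**Stronger readings that a reader might infer.**
- *That the plan discloses the arm to the clinician before step 1.* The text permits this and makes it likely, but does not state it.
- *That effort moves off the clock, so devices look faster and cheaper.* Extra deep stitches would be added untimed work. They replace no part of the timed skin step, so under the step 3 timer the recorded device time need not fall. Under the cost paragraph's definition they could make devices look slower. The documents give no stitch counts or seconds from which to size either effect.
- *That a half-point SBSES gain could arise this way.* As shown above, that is incompatible with the plan's own mean and SD on this scale.

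**Conclusion.** The concern holds as a risk of performance bias, not as a demonstrated error. The plan lets the closing clinician know the arm during two steps meant to be the same in every arm, and it leaves enough discretion in them for technique to differ. SBSES and material cost are exposed under either timer definition; closure time is exposed indirectly under one and directly under the other.

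The size is unknown. The figures of about 6% and 11% at 10 per group, against a nominal 5%, rest wholly on assumed shifts of 0.1 and 0.25 points, an SD of 0.73 in every arm, and no effect of skin closure itself. The documents support no particular shift, and zero is possible. This is a worthwhile minor improvement because it costs so little; the trial's validity does not turn on it.

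**What to change.** 1. **Study Procedures, item 1.** Keep the present opening time. The circulating nurse opens the envelope and operating room staff gather the materials as planned, but the arm is not announced to the closing clinician, and the arm-specific pack is not opened onto the field, until step 2 is complete, just before the timer starts.
2. **Statistical Considerations, item 1.** Amend the no-blinding sentence to match: the closing clinician does not learn the arm until the end of step 2.
3. **Timer.** Reconcile the two start points so that one definition serves both the closure-time outcome and the cost formula.

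The stated reason for early opening is preserved, since the staff who assemble materials still know the arm in time. Sample size, analysis and closure technique do not change.

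The cost is an edit in each of the two sections, plus the timer correction, and a few seconds per case to open the pack. Concealment may sometimes fail, because the clinician may see the supplies being gathered in the same room; partial concealment is still better than none.
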